10 MONITORING

10.1 Data Safety and Monitoring Board (DSMP)

This study has a DSMP. An interim analysis will be done when we have reached 20 patients per group. At this point, the statistician will break the blind, and the PI [name] along with Co-I [name] will review the incidence of pruritus and nausea and vomiting in both groups to examine whether it is higher than expected.

Events will be reported to the IRB according to the "Standard Adverse Event Reporting Guidelines for INTERNAL AEs Occurring at UM". Accordingly, any non-serious unrelated AE, will be reported in aggregate at the IRB continuing review. Serious adverse events (SAEs) will be reported within 14 calendar days if related to the study. SAEs that are NOT related to study participation will be reported in aggregate at scheduled continuing review. Any study-related SAE will be reported within 14 calendar days of becoming aware of the event. Any SAE resulting in death or life-threatening outcome will be reported as soon as possible but not later than 7 calendar days of becoming aware of the event.

DATA HANDLING AND RECORD KEEPING

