1 INTRODUCTION

1.1 Indication

Pruritus is one of the most common and bothersome side effects of intrathecal morphine (ITM) in children, with a reported incidence of 30-70% (1, 2, 13, and 15). We previously found a 40% incidence of pruritus in young children who received intrathecal morphine for major urologic surgery (2) (retrospective review, n= 77, anti-pruritic treatment required in 31 cases). Clinicians, who have witnessed unbearable itching and scratching in their young patients after intrathecal morphine, may be reluctant to offer this effective pain control to future patients, for fear of these unpleasant sequelae.

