2.2 Endpoints

2.2.1 *Primary Endpoint*

Incidence and severity of pruritus within 24 hours post-operatively

2.2.2 *Secondary Endpoint*

- Post-operative nausea and vomiting within 24 hours post-operatively
- Adverse events intra-operatively and within 24 hours post-operatively

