3 STUDY DESIGN

After obtaining IRB approval and informed consent, we will recruit children ages 3-17 years (able to use verbal or pictorial scoring scales) who are scheduled to intrathecal morphine for a surgical procedure and weigh less than or equal to 100kg.

We will recruit 130 children, and randomize using a random numbers table, stratifying for female gender. The patients who have consented to take part in the study, their families and caregivers, their medical team and the trained observers will be blinded to the treatment being given.

Our proposed ondansetron regime comprises an intra-operative bolus dose of ondansetron, 0.1mg/kg IV, prior to intrathecal morphine injection, followed by around-the-clock ondansetron doses, of 0.1mg/kg IV every 6 hours. We will compare this to a standardized control regime comprising an intra-operative bolus dose of saline placebo and around the clock placebo for 24 hours. 56 patients will comprise each group. All children in both groups will be cared for using a standard, current practice, which includes intra-operative anti-emetics per our departmental algorithm for PONV (Postoperative nausea and vomiting), described below.

Rescue orders for pruritus and PONV are also summarized below. See the attached protocol flowsheet for an overview. Naloxone is routinely ordered, to be given as needed for the treatment of respiratory depression or over-sedation only. We will compare our study group with the control group over the 24 postoperative hours with blinded observers / interviewers.

STANDARD OF CARE FOR PONV PREVENTION

As per standard of care, all subjects will receive dexamethasone and diphenhydramine intra-operatively for PONV prevention. For patients who fall into the “High Risk for PONV” category (according to departmental standard of care algorithm), anesthesiologist may, at their discretion, consider any of the following: pre-operatively aprepitant; fluid bolus 30ml/kg; Total Intravenous Anesthesia (TIVA); Sub-hypnotic dose propofol of 1mg/kg infused at 20mcg/kg/min.

STUDY PROCEDURES Pre-Operatively, Intra-Operatively and Post-Operatively:

- **Pre-op:** Patients will be consented in clinic whenever possible or on the day of surgery and randomized, with gender stratification. Patients, their families and health care professionals will be blinded as to whether the patient is in the treatment or control group.

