5.3 Drug Supplies

5.3.1 *Formulation, Preparation and Dispensing*

All study drugs for this study are available on formulary. The study pharmacist will have access to the random numbers table denoting group assignment and will prepare the blinded study drug for each patient and deliver it the appropriate operating room on the day of surgery.

5.3.2 *Drug Storage and Drug Accountability*

All study medications are stored in accordance with Mott OR Pharmacy standards. Drug accountability will be maintained by the study pharmacist and designated and trained Mott OR Pharmacy staff.

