7 ASSESSMENTS

7.1 Primary Endpoint Assessments

For the first 24 hours, subjects will be visited in the PACU, the evening of surgery, the next morning and at 24+/-3 hours (not between the hours of 10p-7a) to obtain the presence and degree of adverse effects, our primary outcomes. Pruritus will be scored similar to previous pediatric studies, as 0 = none; 1 = mild/tolerable/not requiring treatment; 2 = severe/intolerable/requiring treatment (12).

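### The interim review in Section 10.1 shows the PI and a Co-I pruritus and PONV incidence in both groups about a third of the way through the trial, with no margin, PONV rate or action defined

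*Combined protocol and SAP*

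**What the plan says.** Section 10.1 sets one interim analysis, at 20 patients per group. It states: "At this point, the statistician will break the blind, and the PI" together with a Co-I "will review the incidence of pruritus and nausea and vomiting in both groups to examine whether it is higher than expected". It gives no number for what is expected, no margin and no consequence.

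Other sections bear on this:

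- Section 2.2.1 makes the primary endpoint "Incidence and severity of pruritus within 24 hours post-operatively". PONV is a secondary endpoint (2.2.2).
- Section 7.1 defines the top pruritus score as "2 = severe/intolerable/requiring treatment". Section 9.2 contrasts that score with none or mild in the final analysis.
- Section 3 says of the children, families, caregivers and clinicians that "their medical team and the trained observers will be blinded to the treatment being given", and again that "Patients, their families and health care professionals will be blinded as to whether the patient is in the treatment or control group". Neither sentence mentions the interim review.
- Section 1.1 reports a local pruritus rate of 40% from 77 children, with "anti-pruritic treatment required in 31 cases", and a literature range of 30-70%.
- Section 9.1 assumes a halving of the current rate, with 56 per group, but does not say what that rate is.
- Section 11.3.1 provides for continuing or stopping the study on review of serious adverse events only.
- No section gives an expected PONV rate.

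**The concern.** Two things look wrong.

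First, the people leading the trial would see how the two groups compare on the primary endpoint while most of the children are still to be studied. Whether itching is tolerable or needs treatment is a judgement. Knowledge of an interim trend among those who run the trial could affect later scoring, rescue decisions, recruitment or the willingness to continue. The trial is double-blind largely to prevent this.

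Second, the look has no defined use as a safety check. Without a margin, two readers could draw opposite conclusions from the same table. For PONV there is nothing in the protocol to compare the observed rate with. Section 10.1 does not say whether incidence means any itching (score 1 or 2) or only score 2. Whatever the readers conclude, no step follows. The trial takes the risk of disclosure without a defined benefit.

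**Working it through.** **How much of the trial remains.** Section 10.1 gives 20 per group, so 40 children. Section 3 gives 56 per group (112) and 130 recruited.

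- (112 − 40)/112 = 72/112 = 64%.
- (130 − 40)/130 = 90/130 = 69%.

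**Which pruritus rate is expected.** The local figure is 31/77 = 40.3%. For a two-sided 5% test at 80% power (pooled normal approximation), 40% against 20% needs 82 per group, and 56 per group gives 64% power. 50% against 25% needs 58 per group, and 56 gives 79%. The planned 56 therefore fits a current rate near 50% better than the cited 40%. The plan does not settle which rate is expected, so both are carried below.

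**What an undefined margin allows.** Suppose any observed excess over expectation counts. This is one possible reading; the protocol does not state it. Let X be the events among 20 children, binomial, with true rates exactly as hoped (40% control, 20% ondansetron).

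- Control: P(X > 8) = 0.404.
- Ondansetron: P(X > 4) = 0.370.
- At least one arm: 1 − (1 − 0.404)(1 − 0.370) = 0.625.

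So about 62% of trials that are going exactly to plan would show an excess somewhere.

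**A criterion with a margin.** Flag an arm when the exact (Clopper-Pearson) lower 95% limit of its observed rate exceeds a stated expected rate. The smallest counts out of 20 are:

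| Expected rate | Threshold | Lower limit | Chance of a flag if the rate is true |
|---|---|---|---|
| 30% (assumed, PONV) | 11/20 | 0.315 | 0.0171 |
| 40% (pruritus) | 13/20 | 0.408 | 0.0210 |
| 50% (pruritus) | 15/20 | 0.509 | 0.0207 |

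**The same untreated rate for both arms.** With 13/20 in either arm:

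- True 40%/20%: the ondansetron arm almost never reaches 13 (probability about 0.00002), so the chance of a pruritus flag is 2.1%.
- True 40%/40% (inert drug): 1 − (1 − 0.0210)² = 0.042, or 4.2%.
- True 40%/40% with PONV at its assumed 30% in both arms, all four counts taken as independent: 1 − (1 − 0.0210)²(1 − 0.0171)² = 0.074, or 7.4%.

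With 15/20 and a true 50% in both arms, the pruritus figure is 1 − (1 − 0.0207)² = 0.041, or 4.1%.

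**Sensitivity.** The 13/20 threshold is reached with probability 0.13 at a true 50%, 0.42 at 60% and 0.77 at 70%. The 11/20 PONV threshold is reached with probability 0.13 at a true 40% and 0.41 at 50%.

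**Why not a separate expected rate for ondansetron.** Comparing that arm with its hoped-for 20% gives a threshold of 9/20. If the drug is inert at 40%, P(X ≥ 9) = 0.404. Over the four comparisons the chance of a referral is 1 − (1 − 0.0210)(1 − 0.404)(1 − 0.0171)² = 0.437. On the 50%/25% assumption the thresholds are 15/20 and 10/20, P(X ≥ 10) at a true 50% is 0.588, and the total is 1 − (1 − 0.0207)(1 − 0.588)(1 − 0.0171)² = 0.610. Such a rule would mostly detect lack of benefit, not harm.

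**The case against.** The strongest defence is that this is a brief safety look at group totals.

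- **Totals do not reveal any child's allocation.** This stands. Section 5.3.1 says "The study pharmacist will have access to the random numbers table denoting group assignment", and Section 3 concerns knowledge of which group a given patient is in. A reader might infer that Section 10.1 breaches Section 3; the text does not support that.
- **The PI and Co-I may not treat or score, and the table may be coded.** The protocol is silent on both, so bias cannot be asserted. The silence does not remove the risk: Section 10.1 says the blind is broken and does not limit what the two reviewers see.
- **Clinicians would recognise a gross excess without a cut-off, and serious events are reviewed separately.** This stands in part. It is too strong to say that the look could detect nothing. What it lacks is a defined criterion and consequence.
- **The definition and rate can be inferred.** Section 9.2 suggests score 2 and Section 1.1 suggests 40%. That helps for pruritus, although Section 10.1 refers to neither and 56 per group does not follow from 40%. Nothing can be inferred for PONV.
- **A separate monitoring plan may exist.** Section 10.1 says the study has a DSMP, which could be a separate document. If it holds these details, Section 10.1 should refer to it.

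A reader might also infer that the look inflates the type I error. Two unadjusted 5% tests would give about 8.8% overall, but Section 10.1 states no interim test and no efficacy decision, so that figure does not describe this plan.

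**Conclusion.** The concern holds as an avoidable risk of operational bias and as a safety look without a defined use. It does not show that bias will occur, that the blinding rules are broken or that the final test is invalid. The exposure is that 64% (of 112) or 69% (of 130) of the children are studied after the two leaders may have seen the comparison on a judged primary endpoint. Keeping the results with the statistician is the main gain. The missing margin, PONV rate and action would by themselves be missing detail.

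The 62% figure depends on reading the criterion as any excess, and it does not measure bias. The thresholds depend on the expected rate chosen. The 7.4% also depends on an assumed 30% PONV rate and on independence; pruritus and PONV in the same child may well be correlated. Confidence is high on what the text says and moderate on the particular flagging rule.

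**What to change.** Amend Section 10.1 to state the following.

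1. The statistician already named, who must have no part in treating or scoring subjects, keeps the arm-level results. The PI and Co-I receive only a continue/refer statement, without arm-level rates or pooled counts.
2. The flagged event is score 2, as in Section 9.2. Both arms are compared with the same expected untreated pruritus rate, which is the one behind the sample size and should be stated in Section 9.1. For example, an arm is flagged when its exact lower 95% limit exceeds that rate: 13/20 if 40%, 15/20 if 50%.
3. An expected PONV rate is stated and handled the same way (11/20 if 30% is assumed).
4. A flag goes to the IRB with the arm-level table, after confirming that the IRB will accept unblinded data.
5. The look is for safety only and cannot stop for, or claim, efficacy or futility.

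The cost is one wording amendment with IRB approval under Section 11.1. It assumes that the statistician is independent of care and scoring, which the protocol does not state. The PI gives up the mid-trial view of the arms. The flag is weak: at 13/20 it fires 42% of the time at a true 60% and 77% at a true 70%, so it would catch only a large excess. Emergency unblinding under Section 5.2 and the review of serious events are unaffected.

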10.2 CRFs / Electronic Data Record

We will use paper CRFs and data entry will be performed using StatView in a password protected, UM maintained computer. CRFs will be kept in a cabinet in locked research office in the department of pediatric anesthesiology.

10.3 Record Retention

Records will be retained according to IRBMED Guidelines for record retention.

11 ETHICS

11.1 Institutional Review Board (IRB)

Before implementing this study, the protocol, the proposed informed consent form and other information to be provided to subjects, must be reviewed by a properly constituted Institutional Review Board (IRB). Any amendments to the protocol must be reviewed and approved by IRBMED.

11.2 Ethical Conduct of the Study

Subject Information and Consent

The study team member will explain to each subject and parental unit/s (or legally authorized representative) the nature of the study, its purpose, the procedures involved, the expected duration, the potential risks and benefits involved and any discomfort it may entail. Each subject's parent will be informed that participation in the study is voluntary and that he/she may withdraw from the study at any time and that withdrawal of consent will not affect subsequent medical treatment or relationship with the treating physician.

This parental informed consent will be given by means of a standard written statement, written in non-technical language. The subject's parent should read and consider the statement before signing and dating it, and should be given a copy of the signed document. If the subject's parent cannot read or sign the documents, oral presentation may be made or signature given by the subject's legally appointed representative, if witnessed by a person not involved in the study, mentioning that the patient's parent could not read or sign the documents. No patient can enter the study before parental informed consent, as well as child assent, if applicable, has been obtained.

Subjects age 10 years and older will be provided an assent document. An age appropriate discussion of the study will take place and the child will have opportunity to have all questions answered and will sign the document if he/she agrees to participate. A copy will be given to the parent. If the child refuses assent, the subject will not be included in the study.

The informed consent form and pediatric assent forms are considered to be part of the protocol, and will be submitted for IRB approval.

11.3 STUDY DISCONTINUATION CRITERIA

11.3.1 *Stopping Rules for Safety reasons*

The Study team will review all Serious Adverse Events (SAEs) and make recommendations regarding the continuation or discontinuation of the study, as appropriate.

11.3.2 *Rules for Discontinuation of a Subject*

In the event a patient drops out of the study or is discontinued due to protocol violations, all attempts will be made to exit the patient in accordance with the protocol requirements.

APPENDIX A – Protocol Algorithm

PATIENTS RECRUITED:

- 3-17 years and ≤ 100 kg
- Scheduled to have low dose intrathecal morphine for orthopedic or urology surgery

Patients randomized to Control or Study group with gender stratification

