Study Title: A randomized, double-blinded, placebo-control trial of IV ondansetron to prevent pruritus in children who receive intrathecal morphine.
Study Phase: 4
Primary Objective: Demonstrate efficacy of Ondansetron (Zofran) to reduce incidence and intensity of pruritus as a side effect of IntraThecal Morphine (ITM)
Study Design: Prospective, randomized, double-blind, placebo controlled
Study Population: ages 3-17 inclusive
Diagnosis and Main Criteria for Inclusion Each subject must meet the following criteria to be enrolled in this study: Scheduled for any procedure necessitating ITM for pain management. Wt <= 100kg Ability to use verbal or pictorial scoring scales Parental informed consent Subject informed assent, as applicable Subjects who meet any of the following criteria will be excluded from study: Inability to use verbal or pictorial scoring scales (developmental delay) Hypersensitivity to selective 5-HT ₃ receptor antagonists Diagnosed congenital long QT syndrome Severe hepatic impairment Pregnancy and nursing mothers Use of serotonin specific reuptake inhibitors within 14 days Use of serotonergic-nonadrenergic reuptake inhibitors within 14 days Current use of any medications that prolong QT interval
Test Product; Dose; and Mode of Administration: Intervention group: This arm will receive (in a blinded fashion) 0.1 mg/kg of Ondansetron IV diluted in normal saline to a volume of 5 mLs intra-operatively and Ondansetron IV 0.1 mg/kg diluted in normal saline to a volume of 5 mLs every 6 hours for 24 hours postoperatively (not to exceed 40 mg in 24 hours).

Reference or Placebo Therapy; Dose; and Mode of Administration:

Control group:

This arm will receive (in a blinded fashion) a volume-matched placebo (normal saline) intraoperatively as well as IV every 6hrs for 24 hours postoperatively.

Duration of Treatment: Intraoperative time period plus 24 hours from end of surgery.

Statistical Methods:

Data will be summarized using descriptive methods. Parametric data will be analyzed between groups using unpaired t tests or Mann Whitney U, as appropriate. Rankings of pruritus and PONV will be coded as none-mild vs. severe and Chi-squared and Fishers' Exact tests will be used to compare these outcomes between groups. Significance will be accepted at the 5% level.

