1.2 Background and Rationale

The mechanism of morphine-induced itch is not fully elucidated. (1, 16, 19). However, neuraxial opioids induce more frequent and intense itch than peripherally administered doses (26). Centrally located Mu-opioid receptors, in the medullary dorsal horn, may play a role, and activation of this site with an opioid injection induced a dose related scratch frequency in primates (23). The mu opioid receptors, but not other opioid receptor subtypes, appear to mediate the neuraxial opioid-induced itch as opposed to intravenously administered opioids (21, 22, 25). However, the physiology is more complex, as morphine induced pruritus is not always reversed with naloxone (13) and effective treatments for neuraxial induced pruritus include partial opioid agonists (1, 13), 5HT3 antagonists (4-7), propofol (13, 24), and prostaglandin modulation (19).

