4 SUBJECT SELECTION

4.1 Subject Recruitment

4.1.1 *Inclusion Criteria*

1. Age: 3-17 years, inclusive and wt </= 100kg
2. Scheduled for any procedure necessitating ITM
3. Ability to use verbal or pictorial pain assessment tools and techniques
4. Informed consent and assent (if applicable)

4.1.2 *Exclusion Criteria*

1. Inability to use verbal or pictorial scoring scales
2. Hypersensitivity to selective 5-HT₃ receptor antagonists

3. Diagnosed congenital long QT syndrome
4. Current use of any medications that prolong QT interval
5. Severe hepatic impairment
6. Pregnancy or nursing mothers
7. Use of serotonin specific reuptake inhibitors within 14 days
8. Use of serotonergic-noradrenergic reuptake inhibitors within 14 days

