6 STUDY PROCEDURES

6.1 Screening

Subjects will be identified 2 ways:

1. Review of the applicable clinic schedules
2. Review of the daily Operating Rooms schedule

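### Appendix A describes a narrower recruited population (orthopedic or urology surgery, low-dose intrathecal morphine) than the synopsis, Section 3 and Section 4.1.1, and nothing says which text governs

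*Combined protocol and SAP*

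**What the plan says.** Eligibility is described in four places.

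- Synopsis, main criteria for inclusion: "Scheduled for any procedure necessitating ITM for pain management".
- Section 3 (Study Design), on which children will be recruited: "intrathecal morphine for a surgical procedure and weigh less than or equal to 100kg".
- Section 4.1.1, criterion 2: "Scheduled for any procedure necessitating ITM".
- Appendix A (Protocol Algorithm), in its list of patients recruited: "Scheduled to have low dose intrathecal morphine for orthopedic or urology surgery".

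Section 3 also points the reader to a flowsheet: "See the attached protocol flowsheet for an overview". Appendix A is the only appendix and appears to be that flowsheet. Section 6.1 finds candidates from applicable clinic schedules, with no clinic named, and by "Review of the daily Operating Rooms schedule".

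On analysis, Sections 3 and 5.1 stratify the randomization by sex. Section 9.2 codes pruritus as none or mild against severe and compares the groups with chi-squared and Fisher's exact tests. No stratification factor or covariate is mentioned.

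**The concern.** A protocol should give one answer to the question of who may enter. Here the appendix is narrower than the other three places in two respects, surgical specialty and morphine dose. It repeats the same age and weight limits as the formal criteria, so it reads as an entry description and not as loose background.

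The practical risk lies with children who meet the broad description but not the narrow one. One member of staff working from Section 4.1.1 would approach them; another working from Appendix A would not. The narrow description cannot be applied uniformly in any case, because low dose has no definition.

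At stake is a clear statement of the population to which the result applies. The protocol's own background suggests that specialty and dose could be relevant to itch. Section 1.2 reports that "activation of this site with an opioid injection induced a dose related scratch frequency in primates", and the only in-house incidence, in Section 1.1, comes from "young children who received intrathecal morphine for major urologic surgery". Neither statement measures how much specialty or intrathecal dose alters the rate in children.

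**Working it through.** The point is a comparison of text, so the first step sets the four places side by side.

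| Place | Surgery type | Morphine dose | Age and weight |
|---|---|---|---|
| Synopsis | any procedure | no limit stated | 3-17 years, up to 100 kg |
| Section 3 | any surgical procedure | no limit stated | same |
| Section 4.1.1 | any procedure | no limit stated | same |
| Appendix A | orthopedic or urology | low, undefined | same |

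**Step 1: does anything else close the gap?** The eight exclusion criteria in Section 4.1.2 concern scale use, drug hypersensitivity, QT, hepatic function, pregnancy or nursing, and concomitant drugs. None restricts specialty or morphine dose. Section 6.1 names no specialty.

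**Step 2: how are the two rules related?** Every child who fits Appendix A on surgery and dose also fits criterion 2. The narrow group is a subset of the broad one, so the disagreement concerns only the children in the broad group and outside the narrow one. The documents do not say how many there are.

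**Step 3: is any order of precedence stated?** No.

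**Step 4: can an effect on power be worked out?** Section 9.1 gives 56 per group for 80% power and a 50% decrease from a current rate that it does not state. The 5% level comes from Section 9.2; two-sided testing is assumed here, since sidedness is not given. The usual formula, with p̄ the mean of p1 and p2, is

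n = [1.960·√(2p̄(1−p̄)) + 0.842·√(p1(1−p1) + p2(1−p2))]² / (p1−p2)²

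- Section 1.1 reports 31/77 = 40.3%. With 40% against 20%: (1.960 × 0.648 + 0.842 × 0.632)² / 0.20² = 3.249 / 0.04 = 81.2, so 82 per group. Power with 56 per group is about 64%.
- With 51% against 25.5%: (1.960 × 0.687 + 0.842 × 0.663)² / 0.255² = 3.630 / 0.0650 = 55.8, so 56 per group.

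The planned 56 is therefore not reproduced from 40% two-sided (one-sided gives 64). It fits an unstated rate of about 51%. This gap arises from Section 9.1 not stating its baseline. The 40% comes from urology patients, whose surgery type fits both descriptions, so choosing between the descriptions would not close it.

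**Step 5: sex.** Sex is the one factor built into the randomization, and the planned tests ignore it. If sex predicts itch, the unadjusted test remains valid but tends to be conservative and gives up some precision. The documents give no rates by sex, so the gain from adjustment cannot be sized.

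**The case against.** The strongest reply is that three places agree and only an appendix differs. Formal inclusion criteria would ordinarily govern over a flowsheet. Section 3 calls the flowsheet an overview, and does so beside the rescue orders, not as a direction on eligibility. Appendix A gives no consent requirement, scale-use requirement or exclusions, which suggests a summary.

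Most of this stands. The formal criteria probably would govern, although the appendix's omissions carry little weight because part of the flowsheet may be missing from the text available. The reply makes the problem smaller without removing it: the protocol itself sends readers to the flowsheet, the narrower wording is current text, and no precedence is stated.

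A reader might infer more than the documents support:

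- *That the two rules cannot both be followed.* They can. Enrolling only children who fit Appendix A, and who meet the remaining criteria, satisfies all four places.
- *That the criteria expressly allow any morphine dose.* They are silent on dose; the absence of a limit is all that can be said.
- *That the mismatch costs power, as measured over the 30-70% incidence range in Section 1.1.* With 56 per group, exact two-sided chi-squared power for a halving is 48.6% at a 30% control rate, 64.9% at 40%, 78.9% at 50% and 96.5% at 70%. These figures show sensitivity to the control rate. Nothing in the documents ties either end of that range to a specialty, a dose, or one of the two populations.
- *That 40% is the planning rate.* Section 9.1 never says so.

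**Conclusion.** The mismatch is real, is in the current text, and should be corrected. Its size is one of consistency and interpretation: an unknown number of children fall between the two descriptions, and the target population is unclear to that extent. No figure can be put on it, because the documents give neither the case mix nor an event rate for either population.

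It might be inferred that the mismatch biases the treatment comparison. It does not. Whichever children are enrolled, they are randomized and assessed blind, so the comparison between arms remains valid and the unadjusted test in Section 9.2 remains legitimate.

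It might also be inferred that dose variation calls for a primary model adjusted for morphine dose. The documents do not support that. Study drug is given before intrathecal morphine, so the delivered dose is a post-treatment variable. Blinding makes an influence of assignment on dose unlikely, but no section says who sets the dose or when.

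The conclusion assumes that Appendix A is the flowsheet meant in Section 3 and that no text outside the documents sets precedence. It takes no position on which surgery types or morphine doses should be eligible.

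**What to change.** 1. Reconcile the synopsis, Section 3, Section 4.1.1 and Appendix A into one statement covering surgery type and morphine dose. Which rule applies is for the investigators to decide. If a dose qualifier is kept, it must be defined. Cost: a wording amendment.
2. Record surgery type and intrathecal morphine dose per kg on the case report form, and tabulate both by arm, so that the enrolled population can be described. Section 6.2.1 already collects all analgesics used, and weight is needed for eligibility and for study drug dosing. Cost: about two fields.
3. Pre-specify in Section 9.2 a comparison of severe pruritus that respects the stratified randomization, for example a Cochran-Mantel-Haenszel test stratified by sex or a logistic model with treatment and sex. Cost: one sentence and no new data.
4. Label any analysis adjusted for intrathecal morphine dose as exploratory, for the reason given in the verdict.
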